#### 4.1.5 Sample Size Considerations

The dose-escalation phase of the study will enroll 3-6 subjects in each cohort, based on a 3+3 dose-escalation design to assess the MTD level. A maximum of 36 subjects will enroll in the dose-escalation phase.

A maximum of 18 subjects will enroll in the expansion phase (12 additional subjects and the 6 subjects from the dose-escalation phase at the cohort of the highest dose level shown to be well tolerated or the RP2D). The expansion phase sample size of 18 subjects is not based on a formal sample size calculation. Rather, 18 subjects are deemed to be sufficient for the assessment of safety and tolerability as the primary objective and the exploration of clinical anti-tumor activity and other secondary and exploratory endpoints.

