#### 4.1.10 DLT, MTD and RP2D definitions

The MTD is defined as the highest dose studied for which the observed incidence of DLT is less than 33%. Frequencies of toxicities will be tabulated according to the NCI Common Toxicity Criteria version 4.03.

The RP2D will be determined based on the safety data and all available correlative data from the escalation phase by the Safety Monitoring Committee.

Dose-limiting toxicity (DLT) is defined as a clinically significant non-hematologic adverse event or abnormal laboratory value assessed as unrelated to disease progression, intercurrent illness, or concomitant medications and is possibly, probably or definitely related to the study drug and occurring during the first cycle (21 days) on study that meets any of the following criteria:

- All Grade 4 non-hematologic toxicities of any duration
- All grade 3 non-hematologic toxicities. Exceptions are as follow:
  - Grade 3 nausea, vomiting and diarrhea that does not require hospitalization or TPN support and can be managed with supportive care to ≤ grade 2 within 48 hours.
  - Grade 3 electrolyte abnormalities that are corrected to ≤ grade 2 within 24 hours

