Blood collection- pharmacodynamics H	Х	X 			X 		X 		X 		X 	X 									Χ L
Research Bone marrow aspirate/or biopsy	Х											Х									

Notes and abbreviations provided on following page.

- + Subjects enrolled in the Food Effect group will consume a high fat meal within 30 minutes prior to study drug administration on Day 1 blood sample collection.
- § Study drug will be administered without food, at least 1 hour before and at least 2 hours after eating, with the exception of Day 1 of Cycle 1 for subjects enrolled in the Food Effect group.
- ¥ Bone marrow aspirate/biopsy will be performed as clinically indicated, at least once every 3 cycles.
- ‡ Overall Response Rate (ORR) assessment will be performed on the same schedule as bone marrow aspirate/biopsy (every 2-3 cycles during additional cycles). ORR definitions are provided in Section 5.2.2.

<sup>A including Date of Birth; sex; height; race; ethnicity

<sup>B including oncology history, radiation history

<sup>c name, indication, dose, route, start and end dates

<sup>D starting or worsening after study drug administration (signs and symptoms occurring prior to the first dose of study medication on Day 1 should be recorded under the subject's Medical History).

<sup>E complete blood count, differential, platelets

<sup>F glucose, total protein, albumin, electrolytes [sodium, potassium, chloride, total CO₂], calcium, phosphorus, magnesium, uric acid, bilirubin (total, direct), SGPT (ALT) or SGOT (AST), alkaline phosphatase, creatinine, blood urea nitrogen, CPK

<sup>G PT, PTT, fibrinogen, INR

<sup>HOxygen consumption, metabolites, protein, mRNA analysis

<sup>1 To be performed weekly during the first cycle of the increased dose for any intra-subject dose escalation

<sup>1 For purposes of data collection, test results below the limit of quantitation will be reported as "0"

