Pharmacokinetics Blood samples I,K,M		X 	X 	X 	X 	X 	Χ	X 	Χ	Χ	$X_3$	X 	X 	Χ	Χ	X 	Χ	Х	$X^{L}$

Notes and Abbreviations:

<sup>A including Date of Birth; sex; height; race; ethnicity

<sup>B including oncology history, radiation history

<sup>c name, indication, dose, route, start and end dates

<sup>D starting or worsening after study drug administration (signs and symptoms occurring prior to the first dose of study medication on Day 1 should be recorded under the subject's Medical History).

<sup>E complete blood count, differential, platelets

<sup>F glucose, total protein, albumin, electrolytes [sodium, potassium, chloride, total CO₂], calcium, phosphorus, magnesium, uric acid, bilirubin (total, direct), SGPT (ALT) or SGOT (AST), alkaline phosphatase, creatinine, blood urea nitrogen, CPK

<sup>G PT, PTT, fibrinogen, INR

<sup>HOxygen consumption, metabolites, protein, mRNA analysis

<sup>1 To be performed weekly during the first cycle of the increased dose for any intra-subject dose escalation

<sup>1 For purposes of data collection, test results below the limit of quantitation will be reported as "0"

<sup>K If the Investigator determines that the dose of study drug should be interrupted, additional PK, lactate and blood pH assessments will be collected pre-dose (within 2 hours of dosing) and 4 hours +/- 30 minutes post study drug administration upon resumption of dosing; additional PK assessments may be performed during the interruption at the description of the Investigator. If the dose of study drug is reduced, additional PK assessments will be collected pre-dose (within 2 hours of dosing) prior to starting the reduced study drug dose. Additional unscheduled PK, lactate and pH blood draws may be collected per PI judgement when indicated for further safety follow-up.

<sup>L Additional PK and/or PD draws from peripheral blood may be obtained ~every 4 days, when possible, for up to 4 weeks after last study drug administration in subjects who discontinue the study.

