### 4.3.2 Subject Evaluation & Statistics

The FAS will be used for evaluation of safety.

Adverse events will be coded using the MedDRA dictionary. Incidences of treatment-emergent adverse events (TEAE, those events that started after dosing or worsened in severity after dosing) will be presented overall and by maximum severity (according to CTCAE Ver 4.03) and relationship to study medication.

For each continuous laboratory parameter, results will be categorized as low, normal, or high based on the laboratory normal ranges. Frequencies and percentages will be presented by cohort for the shifts in these categories (i.e., low to normal, low to high, high to low, etc.) from baseline to each post-treatment assessment time point. Additionally, for each continuous hematology and chemistry parameter, descriptive statistics will be presented by cohort for the changes from baseline to each post-treatment assessment time point. Descriptive statistics will be presented by cohort for the changes in vital signs from baseline to each post-treatment assessment time point.

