# 5 Subject Eligibility

#### 5.1 Inclusion Criteria

Eligible subjects **must fulfill** all of the following criteria:

1. Subjects with AML should have failed any prior induction therapy regimen or have relapsed after prior therapy (defined as patients in first relapse and less than 12 months from diagnosis [short first remission] or in second or later relapse

Dose-escalation phase: Subjects with confirmed relapsed or refractory AML and no available treatment options with known benefit

Expansion phase: Subjects with relapsed/refractory AML who have failed therapy with up to one prior salvage regimen and no available treatment options with known benefit Exception: stem cell transplant [SCT] or stem cell therapy for subjects who previously underwent SCT/stem cell therapy, and are currently in remission will not be considered a salvage regimen.

- 2. Eastern Cooperative Oncology Group (ECOG) ≤ 2 (see appendix 9.3)
- 3. Patients who have had prior SCT are eligible if they have a relapse > 3 months since autologous or allogeneic stem cell transplantation provided,
  - No clinically significant active graft-versus-host disease (GVHD > grade 1).
  - No treatment with high dose steroids for GVHD (i.e. >20 mg Prednisolone or equivalent per day).
  - No treatment with immunosuppressive drugs with the exception of cyclosporine and tacrolimus.
- 4. Subjects with history of CNS disease are allowed if at the time of day 1 of the study there is no evidence of active CNS disease as documented by negative imaging or spinal fluid analysis carried out at least 2 weeks prior to the first study drug administration in a subject with no clinical signs of CNS disease.
- 5. Adequate renal and hepatic function:
  - Serum creatinine ≤ 2.0 X ULN
  - Total bilirubin  $\leq$  2 times the upper limit of normal (ULN) (or </=3.0 x ULN if deemed to be elevated due to Gilbert's disease or leukemia)
  - ALT and AST ≤ 2.5 times ULN (≤ 5.0 x ULN if due to leukemic involvement).
- 6. Negative urine pregnancy test within 72 hours prior to the first dose of study therapy for women of child-bearing potential (WCBP), defined as a sexually mature woman who has not undergone a hysterectomy or who has not been naturally post-menopausal for at least 24 consecutive months (i.e., who has had menses any time in the preceding 24 consecutive months).

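### The on-treatment chemistry panel asks for ALT or AST although eligibility limits both, so a one-enzyme visit complies with the plan and an isolated rise in the other enzyme could be missed

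*Combined protocol and SAP*

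**What the plan says.** Inclusion criterion 5 (section 5.1) limits both transaminases: "ALT and AST ≤ 2.5 times ULN (≤ 5.0 x ULN if due to leukemic involvement").

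Footnote F to the flowcharts (section 4.2) defines the chemistry row. The relevant part reads "bilirubin (total, direct), SGPT (ALT) or SGOT (AST), alkaline phosphatase", and the words "SGPT (ALT) or SGOT (AST") are the same for cohorts 1-2, cohorts 3-4 and cohorts 5-7. The row is marked at screening and repeatedly on treatment. In the cohort 5-7 flowchart the cycle 1 days are 1, 5, 8, 12, 15, 17 and 21.

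Three rules use these results:

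- **DLT definition (section 4.1.10).** It covers a "clinically significant non-hematologic adverse event or abnormal laboratory value" in the first cycle that is at least possibly drug-related. Its criteria include all grade 4 events and "All grade 3 non-hematologic toxicities", with exceptions only for certain gastrointestinal events and electrolyte abnormalities.
- **Laboratory adverse event rule (section 8.1.1).** A result should be considered an adverse event if it worsens by at least 2 NCI grades from baseline. Five analytes are left to the investigator's judgment of clinical significance; ALT and AST are not among them.
- **Laboratory analysis (section 4.3.2).** Category shifts are planned for each continuous laboratory parameter. In addition, "for each continuous hematology and chemistry parameter, descriptive statistics will be presented by cohort for the changes from baseline".

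**The concern.** The protocol treats ALT and AST as two separate quantities when it decides who may enter, but as interchangeable when it says what to measure. On treatment the flowchart is the only instruction. It does not ask for both, name which one to draw, or ask for the same one each time. A site could follow it exactly and hold no value for one enzyme at a visit, and this would not be a deviation.

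Safety and tolerability are the primary objective, and escalation rests on DLT counts in cohorts of 3 to 6. An incomplete hepatic panel is therefore a gap in a measurement that feeds the main decision. It also leaves the completeness of two planned laboratory summaries to site habit.

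**Working it through.** There is no plan figure to reproduce, and no sample size, power or error rate enters. The check is a comparison of the text.

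**1. Is the mismatch in current text?** Yes. All 3 of 3 flowchart footnotes say *or*; the one eligibility criterion says *and*. These are operative sections, not the amendment log.

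**2. Does anything else close the gap?**

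| Time | Rule that applies | Both enzymes required? |
|---|---|---|
| Screening | Inclusion 5 plus footnote F | Yes, through inclusion 5 |
| On treatment, cycle 1 | Footnote F only | No |
| On treatment, later cycles | Footnote F only | No |

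Sections 4.1.10, 4.3.2 and 8.1.1 use laboratory results but do not say which enzymes to draw.

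**3. What could be missed?** For a DLT to be lost in this way, all of the following must hold:

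- only one enzyme is drawn at the relevant cycle 1 visits;
- the undrawn enzyme reaches grade 3 or higher;
- the drawn enzyme and the rest of the panel (total and direct bilirubin, alkaline phosphatase, CPK) do not prompt further testing;
- the event meets the other conditions of section 4.1.10: clinically significant, not attributed to disease progression, intercurrent illness or concomitant medication, and at least possibly drug-related.

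The documents give a probability for none of these, so their joint probability cannot be stated. The adverse event route in section 8.1.1 needs fewer conditions (a worsening of at least 2 grades), but again only for an enzyme that was not drawn.

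**4. What happens to the tables?** With both enzymes measured at screening, each has a pre-treatment value. A visit with one enzyme then leaves a missing post-baseline value for the other. It does not leave the drawn enzyme without a comparator. This assumes that the screening value may serve as baseline, which section 4.3.2 does not define.

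**The case against.** The strongest reply is that *or* sets a minimum. It does not forbid drawing both, and a single site (section 4.1.4) may run both as routine. That is fair and limits the weight of the point, but the documents do not say what the site does. Relying on habit leaves the measurement outside the protocol.

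Second, the panel always includes bilirubin and alkaline phosphatase, and chemistry is drawn on seven days of cycle 1 in the cohort 5-7 flowchart. Only an isolated transaminase rise, unseen at each relevant visit, is at risk. This stands.

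Third, the laboratory tables are descriptive, and the statistical text before section 4.3 already says that the number of missing values will be presented. This stands too: the loss is of completeness, not of validity.

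Fourth, for much of the trial the edit comes too late. The amendment log records a safety committee recommendation at the end of cohort 4 under the January 2019 amendment, and the current version is dated January 2020. Cycle 1 data for cohorts 1 to 4 cannot be changed. This stands, and it makes the cohort 5-7 flowchart the one that matters.

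**Conclusion.** The inconsistency is real but small. On treatment the plan permits one transaminase where eligibility names two. A qualifying isolated rise in the other could be missed, and the laboratory tables could lack some post-baseline values. The size cannot be given: it depends on how often only one enzyme is drawn and how often the two disagree, and the documents report neither.

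Three stronger readings are tempting and are not supported:

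- *Eligibility depends on which enzyme is drawn.* It does not. Inclusion 5 binds both, so a subject with one result has not been shown to be eligible.
- *Change from baseline has no matched baseline.* Screening should supply a value for each enzyme, whichever is drawn later.
- *DLT counts are distorted.* Under section 4.1.7 a single event does separate 0 of 3 from 1 of 3, and 1 of 6 from 2 of 6. But a grade 3 enzyme value is not automatically a DLT, and nothing shows that such an event was or would be missed. The counts mark where one event would matter; they are not an estimate of effect.

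**What to change.** In footnote F, replace *or* with *and*, so that the chemistry panel lists both ALT and AST and agrees with inclusion criterion 5. The flowchart for cohorts 5-6 and cohort 7 is the priority, because it can still affect data collection; the other two should be aligned for consistency.

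The cost is one word per footnote and at most one more analyte on a chemistry sample already drawn. If the site already runs both, the edit only documents practice.

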### Study Objectives & Endpoints

Primary Objectives	Safety & Tolerability
	Determine Dose Limiting Toxicities
	Establish MTD and RP2D
Secondary Objectives	IACS-010759 pharmacokinetics and food effect
	Preliminary Clinical Efficacy (overall response rates, duration of
	response, progression-free survival, overall survival)
Exploratory objectives	Pharmacodynamic and exploratory biomarkers of activity of IACS-
	010759

Clinical study data will be entered into Medidata Rave, the clinical data base, via electronic case report forms. The Statistical Analysis Plan (SAP) will include detailed and specific description of all analysis to be performed on the clinical data from this study. The SAP will be finalized prior to database lock.

All statistical analyses will be performed using Version 9.4 or later of Statistical Analysis Software (SAS®). Data summaries will use descriptive statistics (number of subjects [n], mean, standard deviation [SD], Q1, median, Q3, minimum, and maximum) for continuous variables, and frequency and percentage for categorical and ordinal variables. If there are missing values, the number missing will be presented, but without a percentage. All data collected will be included in by-subject data listings.

Unless otherwise specified, all tests will be two-tailed using a 0.05 level of significance. All confidence intervals (CIs) will be two-sided 95% confidence intervals.

All subjects who received any study drug and who had any on-treatment evaluation will be included in the Full Analysis Set (FAS).

### 4.3 Safety and tolerability

### 4.3.1 Endpoints & Assessment Methods

Laboratory tests, vital sign measurements, physical exams and subject interviews will be performed to detect new abnormalities and deteriorations of any pre-existing conditions. All "treatment-emergent" clinically significant abnormalities and deteriorations that begin or worsen in severity after initial administration of IACS-010759 and documented as such in the medical records should be recorded in the Case Report Forms as Adverse Events and graded according to the National Cancer Institute Common Terminology Criteria for Adverse Events (CTCAE) v4.03.

The MTD will be determined in accordance with Section 4.1.7.

### 4.3.2 Subject Evaluation & Statistics

The FAS will be used for evaluation of safety.

Adverse events will be coded using the MedDRA dictionary. Incidences of treatment-emergent adverse events (TEAE, those events that started after dosing or worsened in severity after dosing) will be presented overall and by maximum severity (according to CTCAE Ver 4.03) and relationship to study medication.

For each continuous laboratory parameter, results will be categorized as low, normal, or high based on the laboratory normal ranges. Frequencies and percentages will be presented by cohort for the shifts in these categories (i.e., low to normal, low to high, high to low, etc.) from baseline to each post-treatment assessment time point. Additionally, for each continuous hematology and chemistry parameter, descriptive statistics will be presented by cohort for the changes from baseline to each post-treatment assessment time point. Descriptive statistics will be presented by cohort for the changes in vital signs from baseline to each post-treatment assessment time point.

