- 2. If lactic acid >ULN but below 4.0 mmol/L, and subject is symptomatic (nausea, vomiting, generalized muscle weakness, tachycardia, hypotension and rapid breathing), treatment should be interrupted as indicated and lactic acidosis workup performed.
- 3. If lactic acid is above 4.0 mmol/L, blood pH ≥7.35 and bicarbonate (reported as total CO2) is <LLN, potassium is normal and anion gap <14, and subject is asymptomatic, dosing should be interrupted. Lactic acid and blood pH and electrolytes should be reassessed within 12 hours on arterial and/or venous blood draw until the lactic acid level is <4.0 mmol/L. Once the lactic acid level is <4.0 mmol/L on arterial and/or venous draw, the subject can continue therapy at the discretion of the investigator.
- 4. If lactic acid is above 4.0 mmol/L, blood pH <7.35 if the baseline pre-therapy pH was >7.35 or blood pH <7.30 if the baseline pre-therapy pH was ≤7.35) and the bicarbonate (reported as total CO₂) is <LLN and anion gap is elevated, and/or the subject is symptomatic, this will be considered a DLT. Treatment should be interrupted and lactic acidosis workup performed (See Section 7.2.3).

Anion gap via venous blood collection can be calculated as follows: Anion Gap= [Na+] - [Cl-] - [total CO2]; normal range 4-14 mmol/L.

Anion gap via arterial blood collection can be calculated as follows: Anion Gap= [Na+] - [Cl-] - [HCO3-]; normal range 8-16 mEq/L.

Symptoms of lactic acidosis include nausea, vomiting, generalized muscle weakness, tachycardia, hypotension and rapid breathing. Subjects with clinical symptoms concerning for lactic acidosis should have an arterial blood gas assessment. Lactic acidosis is characterized by an elevated blood lactate concentration [>4.0 mmol/L]), decreased blood pH (<7.35), and electrolyte disturbances with an increased anion gap.

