### 7.2.2 Use of Blood Products

During the administration of IACS, subjects may receive red blood cell (RBC) or platelet transfusions, if clinically indicated, per institutional guidelines.

Myelosuppression is expected in subjects with AML due to underlying disease. Most subjects will have neutropenia, thrombocytopenia, or both at study entry. Significant or life-threatening myelosuppression may be managed with growth factor support including G-CSF, GM-CSF and platelet growth factors and erythropoietin/darbopoietin/blood transfusion according to institutional standard of care, American Society of Clinical Oncology (ASCO) Practice Guidelines, and/or NCCN Practice Guidelines.

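### Laboratory tables in section 4.3.2 show neither the CTCAE grade reached nor the protocol's own lactate and pH cut-offs

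*Combined protocol and SAP*

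**What the plan says.** Section 4.3.2 plans two laboratory summaries. In the first, for each continuous parameter, "results will be categorized as low, normal, or high based on the laboratory normal ranges". It continues: "Frequencies and percentages will be presented by cohort for the shifts in these categories", from baseline to each later time point. The second is narrower: "Additionally, for each continuous hematology and chemistry parameter, descriptive statistics will be presented by cohort for the changes from baseline". The Study Objectives & Endpoints section defines the descriptive statistics as the number of subjects, "mean, standard deviation [SD], Q1, median, Q3, minimum, and maximum) for continuous variables", and puts all collected data in by-subject listings.

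Treatment-emergent adverse events "will be presented overall and by maximum severity (according to CTCAE Ver 4.03) and relationship to study medication". Section 8.1.1 lists when a laboratory result should count as an adverse event. The triggers are withdrawal or withholding of treatment, an intervention, investigator judgment, or a rise of at least 2 CTCAE grades from baseline. A few tests are excepted from the 2-grade trigger; neutrophils and platelets are not among them.

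On the state of subjects at entry, section 7.2.2 says: "Most subjects will have neutropenia, thrombocytopenia, or both at study entry". In the section 4.2 flowcharts, lactate and blood pH have their own row. The chemistry panel in footnote F ("glucose, total protein, albumin, electrolytes [sodium, potassium, chloride" and so on) contains neither.

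**The concern.** Safety and tolerability is the primary objective. Two kinds of laboratory change matter most here: further loss of counts that are already low, and lactic acidosis, which section 4.1.11 treats as a toxicity to be expected from the drug's mechanism. A low/normal/high table is least informative for both. A count that starts below the normal range has no lower category to move to. A lactate just above the upper limit of normal (ULN) shares a cell with one well above the DLT threshold.

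The tables also run by time point, and no worst on-treatment value is planned. Section 4.1.11 calls for repeat pH and lactate draws at 6, 12 and 24 hours in some subjects and reassessment within 12 hours in others, and flowchart footnote K allows unscheduled draws. Section 4.3.2 does not say how such values enter a table organised by scheduled visit, so the peak of an episode could be absent from it.

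At stake is how well the laboratory tables describe toxicity by regimen when the RP2D is chosen and the results are reported.

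**Working it through.** The plan attaches no figure to this point, so there is none to reproduce. The check applies the three-category rule to values on either side of the protocol's own thresholds.

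**Inputs from the protocol.** ANC 0.5 and platelets 20 x10^9/L (section 4.1.9.1; the ANC threshold is also in the myelosuppression DLT of 4.1.10). Lactate 4.0 mmol/L and pH 7.35, 7.30 and 7.2 (4.1.10 and 4.1.11). Screening exclusion values of lactate above 2 mmol/L and pH below 7.35 (5.2).

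**Assumed inputs.** The documents give no laboratory normal limits, so ranges were used: ANC lower limit 1.5 to 2.0 and platelet lower limit 140 to 150 x10^9/L, lactate ULN 1.6 to 2.2 mmol/L, pH 7.35 to 7.45.

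**Step 1: classify.** Rule: low if below the lower limit, high if above the upper limit, otherwise normal. The result is the same for every limit tried in the assumed ranges.

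| Parameter | Values | Category |
|---|---|---|
| ANC (x10^9/L) | 1.2, 0.9, 0.4, 0.1 | all low |
| Platelets (x10^9/L) | 60, 45, 19, 8 | all low |
| Lactate (mmol/L) | 2.3, 3.9, 4.1, 9.0 | all high |
| pH | 7.34, 7.31, 7.29, 7.21, 7.05 | all low |

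A fall through ANC 0.5 or platelets 20 is therefore recorded as low-to-low. Because of the screening limits, most lactate and pH values should start near normal. The table will then show that a subject left the normal range, but not on which side of 4.0, 7.35 or 7.30 the subject ended.

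**Step 2: reach of the shift table for counts.** The documents do not give the share of subjects with low platelets at baseline. If it is 60% to 90% (assumption), the table can register a move down into the low category in at most 1 - 0.90 = 10% to 1 - 0.60 = 40% of subjects. In a cohort of 6 that is 0.6 to 2.4 subjects. This describes that one table, not the whole plan.

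**Step 3: what change from baseline adds.** Take six hypothetical ANC changes: 0, 0, 0.1, -0.1, 0, -0.9. The mean is -0.9/6 = -0.15, the median 0 and the minimum -0.9. The planned minimum does show the fall. It does not show where the fall started: from 1.3 it ends at 0.4, below 0.5; from 2.9 it ends at 2.0, not below any lower limit assumed here.

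**Step 4: what the adverse event route adds.** A fall from grade 2 to grade 4 is a 2-grade rise in severity, so it should be recorded as an adverse event and enter the table by maximum severity. A move from grade 3 to grade 4 is one grade, so capture depends on an intervention, withholding or judgment. Section 4.1.9.1 plans no interruption for myelosuppression in the first 4 cycles, so withholding will seldom be the trigger.

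**Step 5: lactate and pH.** Change from baseline is promised for hematology and chemistry parameters. Footnote F omits lactate and pH, and the flowchart gives them a separate row. Read literally, only the three-level shift applies to them. If the sponsor does count them as chemistry, they also get change-from-baseline statistics, but still no split at the cut-offs.

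**The case against.** The strongest reply is that the shift table is one display among several. Hematology has change-from-baseline statistics with a minimum and maximum. Multi-grade worsening becomes a graded adverse event. Lactate above 4.0 mmol/L in the combinations that interrupt dosing under 4.1.11 also becomes an adverse event, because withholding treatment is a trigger. Every value is listed, and with 3 to 6 subjects per escalation cohort a listing can be read by dose. That chemistry excludes lactate is inferred from the flowchart. The Study Objectives & Endpoints section also leaves detailed analyses to an SAP to be finalized before database lock.

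Most of this stands, and it rules out three stronger readings that a reader might reach:

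- *The plan would miss worsening of low counts.* It would not: change from baseline and the 2-grade trigger catch much of it.
- *Lactate and pH have no other summary, so nothing could be said about them by dose.* Adverse event tables and listings also carry them.
- *DLT or MTD calls are compromised.* They are judged per subject against 4.1.10 and 4.1.11, not from these tables.

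What remains is a gap in the laboratory tables. Listings are not a summary. Asymptomatic lactate between ULN and 4.0 mmol/L with pH above 7.35 continues on treatment and need not become an adverse event. Section 4.3.2 specifies presentation by cohort for the laboratory tables but not for adverse events. A later SAP may close the gap, but the supplied text does not.

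**Conclusion.** The point holds as a limited gap in presentation. The supplied text plans no laboratory shift by CTCAE grade, no worst on-treatment value, and no tabulation of lactate or pH at the protocol's cut-offs. For counts, what is mainly lost is one-grade worsening from an already low baseline. For lactate and pH, it is the size of the abnormality relative to 4.0 mmol/L, 7.35, 7.30 and 7.2.

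The classification in step 1 rests on assumed normal limits but does not change across the ranges tried. The 10% to 40% figure rests on an assumed baseline rate and must not be read as the share of declines that the plan detects. The lactate and pH part rests on a literal reading of chemistry as the footnote F panel. This is a worthwhile, inexpensive improvement to the display of the primary safety objective; it is not a flaw in dose-escalation decisions.

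**What to change.** In section 4.3.2, keep the by-time-point low/normal/high shifts, which show the time course, and add by cohort or regimen:

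- **(a)** For parameters that can be graded, a shift table from baseline grade to worst on-treatment CTCAE v4.03 grade.
- **(b)** For lactate and blood pH, change-from-baseline statistics and a tabulation of the worst on-treatment value, with unscheduled draws included. Lactate bands: up to ULN, above ULN to 4.0, above 4.0 mmol/L. pH bands: 7.35 or above, 7.30 to below 7.35, above 7.2 to below 7.30, 7.2 or below. Show pH by baseline above 7.35 or at most 7.35, because the second lactic acid criterion in 4.1.10 depends on it. Given the screening limit, the lower baseline group may be small.

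These bands are for tabulation only, use cut-offs already in the protocol, and change no clinical rule. Lactate 4.1 and 9.0 mmol/L still share the top band; the maximum change from baseline helps show the difference. Worst values tend to look worse with more draws, another reason to keep the scheduled-visit tables alongside.

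The cost is SAP wording and a few extra table shells. No new data are needed.
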